
Statistical analysis
	
Efficacy: The objective of the trial is to prove superiority of the intervention arm versus the control arm. The primary analysis follows from the chosen adaptive design with one unblinded interim analysis after follow-up of 50% of the patients.
 
Description of the primary efficacy analysis and population: The primary analysis will follow the intention to treat (ITT) principle in the FAS (Full Analysis Set); that includes all randomised patients, as belonging to their randomisation arm, regardless of whether awake prone positioning could be applied as intended, or whether other protocol deviations are known. All details on the analyses will be detailed in a statistical analysis plan, which will be finalised prior to inclusion of the first patient. The adaptive analysis strategy for the primary endpoint follows the Inverse Normal method to independent test statistics derived from models on per-stage data. Each analysis (interim and final) will consist of a mixed logistic regression model comparing the primary outcome "tracheal intubation or all-cause death" between random groups with age and mode of respiratory support at inclusion as fixed effects and centre as random effect in order to map the stratified randomisation scheme. One-sided significance bounds for the two analyses are 0.0026 and 0.024. Overall, an alpha of 0.025 one-sided will be spent on the primary outcome.

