	
Effect size assumed for power calculation: The sample size and power calculation are based on previous knowledge, assuming a 28-day event rate of the combined endpoint in the control group of 50%, and a reduction to 35% in patients with the experimental intervention. To account for possible imprecision regarding the assumptions, an adaptive design was chosen with one interim analysis after follow-up of 50% of the planned number of patients, in order to allow stopping early for futility or efficacy and to re-estimate the sample size. Based on these assumptions and for an overall one-sided type-one error of 2.5% and statistical power of 80%, 171 patients per group (342 overall) are planned to be enrolled to prove superiority. The maximum sample size will be restricted to 513 patients.
 
Safety: Rates of adverse events and serious adverse events will be tabulated by treatment group, according to type of event and system organ class. Safety endpoints for the APP group will be analysed descriptively (event rates with two-sided 95% confidence intervals).
 
Secondary endpoint(s): Treatment effects will be calculated with two-sided 95% confidence intervals and are of descriptive nature only. Secondary outcomes will be analysed depending on the scale type, corresponding to the primary analysis. Percentage of patients meeting key safety endpoints, as well as assessment of adverse events.

Safety:	To be randomized into the trial: n = 342 To be analysed: n = 342 – intention to treat analysis Adaptive sample size: n = 342 - 513
Number of Patients	
Note: adaptive sample size (see below for details)
 
Note: recruitment will be competitively among sites (currently 20 sites planned)

Table 1. STUDY SCHEDULES

Phase of study	Screening & Randomisation	Visit 2	Visit 3
Point in time	Day 1	Day 1-3	Day 28 (± 3 days)
Informed Consent	✓		
I/E Criteria	✓		
Medical History & Demographics	✓		
Vital Signs	✓	✓	
Routine laboratory values (blood count)	✓	✓	
Routine blood gas values	✓	✓	
Parameters of oxygenation and oxygenation therapy (HFNO, NIV, CPAP)	✓	✓	
Start of Intervention (Prone Positioning) therapy	✓	✓	
Endpoints	✓	✓	✓

Figure 1. Trial Flow

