9.3.3.4 Criteria for Termination of the Study

The PROSA trial will be supervised by its Steering Committee and an independent Data Safety Monitoring Board (DSMB). All final decisions, however, regarding study termination or modification will be agreed with the Steering Committee and the independent DSMB.

No formal stopping rules will be set. An independent DSMB will monitor safety in the trial. Should safety concerns evolve, they should recommend stopping the study. Stopping the trial for efficacy or futility is an option.

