9.7.1.2.2 Statistical Analyses

All statistical analyses will be carried out by the trial statistician. To preserve the blinding of the study's biometry team until the final analysis, the unblinded interim analysis will be conducted by a separate biometry team from the same institute. Baseline variables will be described by treatment group using appropriate summary statistics.

9.7.1.2.2.1 Primary, Secondary, and Safety Endpoints

The primary efficacy analysis will be performed according to the ITT principle and will therefore be based on the FAS. The adaptive analysis strategy for the primary endpoint follows the Inverse Normal method to independent test statistics derived from adjusted mixed logistic regression models on per-stage data obtained. This strategy allows the use of conventional stopping strategies of group sequential designs. Unbiased parameter estimates and confidence intervals can be obtained by using the theory of repeated confidence intervals. In detail, the null hypothesis will be tested at overall one-sided type-one error of 2.5% with stopping boundaries according to an O'Brien and Fleming α -spending function. To account for the adaptive design of the trial, the Inverse Normal method will be used with weights $w_1=w_2=\sqrt{0.5}$ at the interim and final analysis, respectively. The test on treatment difference at each stage k ($k=1,2$) will be based on a Wald test statistic originating from a mixed logistic regression model including the treatment group (intervention versus control alone), age and respiratory status at randomization fixed effects and centre as random effect to reflect the stratified randomization. To ensure that the stage-wise test statistics are independent, the data are divided into two subsets, a first-stage and a second-stage data set.

Interim analysis:

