After follow-up of 50% of the planned patients, an interim analysis with the possibility to stop for efficacy or futility will be conducted. The treatment effect is tested using the Inverse Normal method applied to the Wald test statistic (originating from the adjusted mixed logistic regression model) at interim significance level which is determined by an O'Brien and Fleming type α -spending function. If the trial is continued to stage 2, the sample size re-calculation will be based on conditional power, with a target conditional power of 80%. After re-calculation, the sample size is adjusted with the originally calculated sample size and the maximum sample size of 342 as lower and 513 upper limit for the adjusted sample size.

Final analysis:

The second-stage data for the final analysis will be based on the Inverse Normal combination of the Wald statistics from the adjusted mixed logistic regression models of the first- and second-stage data

(with weights $w_1=w_2=\sqrt{0.5}$) at local significance level according to the α -spending function. Parameter estimates and confidence intervals are calculated based on the theory of repeated confidence intervals (RCI), where the midpoint of the two-sided RCI is used as point estimate.

Secondary endpoints: Secondary efficacy endpoints will be analysed in the FAS. Treatment effects will be calculated with two-sided 95% confidence intervals. P-values and confidence intervals derived from these analyses are of descriptive nature only. Secondary outcomes will be analysed depending on the scale type. Time-to-event outcomes will be analysed by Cox proportional hazard models including centre as frailty term. Dichotomous variables will be tested by mixed logistic regression with centre as random effect. Continuous variables will be analysed with linear mixed effects models that include the baseline determinations of the outcome and centre as random effect. Scale transformations will be considered based on the pooled data set. In further secondary analyses, the effect of the number of hours with awake prone positioning on the primary and secondary endpoints is evaluated for the intervention group.

Safety endpoints: Safety analyses will be performed in the EFS. Rates of adverse events and serious adverse events will be tabulated by treatment group, according to type of event and system organ class.

9.7.1.2.2.2 Dropouts

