9.7.1.3 Proposed Sample Size

Sample size calculation was performed with rpact 3.3.4, R version 4.2.3 [Wassmer G, Pahlke F (2023). rpact: Confirmatory Adaptive Clinical Trial Design and Analysis. R package version 3.3.4, <https://CRAN.R-project.org/package=rpact>] using the test for two proportions using the Z-test with unpooled variance. The sample size and power calculation are based on previous similar trials in COVID-19, international ICU databases, observations from small proof-of-concept studies, as well as from our own hospital-based patient information system (3, 9, 12, 14, 15). Based on these data, we estimate the relative decrease of 28-day mortality / need for tracheal intubation by our intervention compared to standard-of-care by 30%. Patients with acute hypoxemic respiratory failure on ICU, as shown by previous studies and own databases, display a 28-day event rate of the combined endpoint of 50%, so that we assume a reduction to a 28-day event rate of 35% in patients with the experimental intervention for sample size calculation (3, 9, 12, 14, 15).

Due to lack of appropriately large data sets, the current assumptions may comprise a certain imprecision. To account for this imprecision, an adaptive design was chosen with one interim analysis (O'Brien and Fleming boundary) after follow-up of 50% of the planned number of patients, in order to allow stopping early for futility or efficacy and to re-estimate the sample size. Only an independent statistician will be unblinded for this purpose and unblinded data will only be reported to the DSMB (including the DSMB statistician). The Sponsor and all other study team members stay blinded till the end of the study.

Based on these assumptions and for an overall one-sided type-one error of 2.5% and statistical power of 80%, 171 patients per group (342 overall) are planned to be enrolled to prove superiority. To avoid an unmanageably large sample size, the sample size after recalculation will be restricted to a maximum of 513 patients (chosen based on practical reasons including feasibility of enrolment and a clinically meaningful effect).

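### The protocol calls estimates from repeated confidence intervals unbiased, but the interval midpoint it reports is biased when the trial may stop early

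*Protocol*

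**What the plan says.** Section 9.7.1.2.2.1 of the protocol combines stage-wise Wald statistics from adjusted mixed logistic models by the inverse normal method with equal weights. On estimation it says: "Unbiased parameter estimates and confidence intervals can be obtained by using the theory of repeated confidence intervals". Under the final analysis it specifies that "the midpoint of the two-sided RCI is used as point estimate". No other estimator is named for the primary endpoint.

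The same section provides for early stopping: "an interim analysis with the possibility to stop for efficacy or futility will be conducted". If the trial continues, the total is re-calculated for 80% conditional power, between 342 and 513 patients. Section 9.3.3.4 adds: "Stopping the trial for efficacy or futility is an option". No numerical futility bound is given, nor is it stated which effect enters the conditional power. The synopsis gives the efficacy bounds: "One-sided significance bounds for the two analyses are 0.0026 and 0.024".

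**The concern.** An RCI has at least nominal coverage at each look, whether or not the stopping boundary is obeyed. That is a property of the interval. It does not make the centre of the interval an unbiased estimate.

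If the trial stops at the interim, the midpoint is the raw first-stage estimate, which is being reported because it was extreme. If the trial continues, the midpoint is a weighted average of the two stage-wise estimates, with no adjustment for having passed an interim look. The protocol therefore attributes to its headline odds ratio a property it does not have. This matters most after an efficacy stop, when the reported effect is expected to be too large and the protocol gives no warning.

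**Working it through.** **Inputs from the protocol.** Event rates 50% and 35%, 1:1 allocation, 342 patients, interim at 50% (171 patients, 85.5 per arm), weights √0.5, one-sided bounds 0.0026 and 0.024, re-calculated total 342 to 513. Benefit is counted as positive, so the true log OR is ln[(0.50/0.50) × (0.65/0.35)] = 0.619 (OR 0.54).

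**Assumptions not in the protocol.** Conditional power at the observed effect unless stated; futility bounds none, Z1<0, Z1<0.5 or Z1<1; simple two-arm Wald statistics in place of the mixed model.

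**The plan's own figures.** Classical O'Brien-Fleming bounds for two equally spaced looks give one-sided levels of 0.0026 and 0.0240, as printed. With the unpooled two-proportion Z-test they need 168 per group (336 overall). The planned 171 per group (342) gives 80.7% power. The design reproduces.

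**The estimator.** Let e1, e2 be the stage-wise log ORs and se1, se2 their standard errors. The printed levels correspond to c1 = 2.794 and c2 = 1.977.

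- Interim stop: the RCI is e1 ± c1·se1, so its midpoint is e1.
- Final look: the RCI contains all θ with |√0.5·[(e1−θ)/se1 + (e2−θ)/se2]| ≤ c2, so its midpoint is (e1/se1 + e2/se2)/(1/se1 + 1/se2).

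**First-stage precision.** se1 = √[(1/0.50 + 1/0.50 + 1/0.35 + 1/0.65)/85.5] = √(8.396/85.5) = 0.313.

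**Interim efficacy stop at the planned effect.**

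- Smallest estimate that crosses: 2.794 × 0.313 = 0.875, an OR of about 0.42.
- Probability: with a = 2.794 − 0.619/0.313 = 0.82, 1 − Φ(a) = 0.206.
- Mean estimate given a stop: 0.619 + 0.313·φ(a)/[1 − Φ(a)] = 0.619 + 0.313 × 0.285/0.206 = 1.05, an OR of 0.35. The log OR is about 70% too large (0.43/0.619).

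**Efficacy stop only, fixed size.** The midpoint is e1 after a stop and (e1+e2)/2 otherwise, so the mean bias is se1·φ(a)/2 = 0.313 × 0.285/2 = +0.045, about 7%. Simulation gives +0.045 (7.3%). With neither stopping nor re-calculation the bias is zero; re-calculation alone gives +0.010 (1.6%).

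**Efficacy stop with re-calculation, no futility stop.** Stopped trials (20.6%) average 1.0527 and continuing trials 0.5756, which is 0.043 below the truth. The overall mean is 0.206 × 1.0527 + 0.794 × 0.5756 = 0.674, a bias of +0.055 (8.9%). With conditional power at the planned effect it is +0.053 (8.6%). The median bias is about +0.013.

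**Dependence on the futility rule and the true effect** (efficacy stop and re-calculation, mean bias on the log OR; separate runs differ only in the last digit):

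| True rates | No futility stop | Z1<0 | Z1<0.5 | Z1<1 |
|---|---|---|---|---|
| 50% vs 35% | +0.055 (8.9%) | +0.044 (7.1%) | +0.030 (4.9%) | +0.009 (1.4%) |
| 50% vs 40% | +7.4% | −0.1% | −5.5% | not run |
| 50% vs 50% | +0.004 | −0.068 | −0.060 | not run |

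**Check on binomial data** (50% vs 35%, no futility stop): log OR bias +8.5%; mean risk difference 16.4 points against a true 15.

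**The interval.** RCI coverage at the planned effect is 97.0% without a futility stop and up to 98.2% with Z1<0.5. It is valid and conservative.

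**A median-unbiased estimate from stage-wise ordering** (planned effect, re-calculation, no futility stop): mean bias 6.4% against 8.9% for the midpoint, median bias 0.000 against 0.013, interval coverage 95.0% against 97.0%, mean interval width 0.92 against 1.00. After an interim stop the two point estimates are identical.

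**The case against.** The strongest reply is that the fault is one adjective in a general sentence. The operative rule, RCI with midpoint, makes no claim of unbiasedness, is prespecified and matches the test. The interval also protects the reader. After an efficacy stop with the average estimate, the RCI is 1.05 ± 0.875 on the log scale, an OR from about 0.15 to 0.84, which contains 0.54; coverage given such a stop is 98.7%. The overall mean bias of 0.055 is about one fifth of the estimator's standard deviation (0.258). A median-unbiased estimate is no cure for an interim stop, and it is valid only if the bounds are followed, which section 9.3.3.4 does not guarantee. Supplementary estimators also commonly belong in the SAP, which is not shown.

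Much of this stands. The interval is sound, the overall bias is moderate, its sign cannot be fixed while the futility rule is open, and the supportive estimate helps only modestly. None of it makes the sentence true, and an SAP that follows the protocol would carry the error forward. Reading the word as median-unbiased does not rescue it either: with an assumed stop at Z1<0 and no true effect, the median bias is −0.055.

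The size depends somewhat on the bounds. An O'Brien-Fleming type spending function, as section 9.7.1.2.2.1 words it, gives 0.0015 and 0.0245 rather than the printed levels. The chance of an interim stop then falls to 16% and the mean bias to about 0.048 (7.8%). The conclusion is unchanged.

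**Conclusion.** The concern holds. The RCI is valid, but its midpoint is not an unbiased estimate under this design. At the planned effect the mean overstatement of the log OR runs from 1.4% to 8.9% over the assumed futility rules; at smaller true effects a futility stop can reverse the sign. Given an interim efficacy stop, the log OR is about 70% too large on average. These figures rest on a normal approximation with simple two-arm Wald statistics and on the assumed conditional-power and futility rules. The bias from the efficacy stop alone (about 7%) needs neither of the last two. The hypothesis test, type I error and sample size are not affected, so this should be corrected but does not threaten the confirmatory decision.

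**What to change.** In section 9.7.1.2.2.1, replace the general sentence with wording such as: *Repeated confidence intervals have at least nominal coverage at each look; the interval midpoint is not an unbiased estimate of the treatment effect.*

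Under the final analysis, keep the RCI and its midpoint as primary and add: *A median-unbiased estimate with a 95% interval from stage-wise ordering, computed from the same stage-wise Wald statistics, is reported beside it as supportive. It is valid only if the efficacy boundary and any futility bound were followed. After an interim efficacy stop both point estimates coincide and are expected to overstate the effect.*

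The cost is two wording changes and one extra estimate from statistics already computed. Alpha, bounds, sample size and conduct do not change. The second estimate is slightly less favourable at the planned effect (OR 0.517 against 0.510, from the mean log ORs), lowers the mean bias only modestly and does not correct an interim stop. The correction of the first sentence is needed even if the supportive estimate is declined.

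### The primary model omits baseline hypoxaemia severity, which is already recorded before treatment; adding SpO2/FiO2 as one pre-specified covariate is a valid, nearly cost-free gain in precision

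*Protocol*

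**What the plan says.** The protocol names the primary model's covariates twice. Section 9.7.1.2.2.1 gives treatment plus "age and respiratory status at randomization fixed effects and centre as random effect to reflect the stratified randomization". The Synopsis (Statistical analysis) gives the same structure, "with age and mode of respiratory support at inclusion as fixed effects and centre as random effect", and also explains it by the randomisation scheme. Section 9.4.2 confirms the stratification factors: centre, age and mode of respiratory support.

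Section 9.3.1 admits patients with PaO2/FiO2 of at most 300 mmHg or SpO2/FiO2 of at most 315, on HFNO, NIV or CPAP with FiO2 of at least 40%. Table 1 schedules vital signs, blood gases and the row starting "Parameters of oxygenation and oxygenation therapy (HFNO, NIV, CPAP" at screening and randomisation. Section 9.5.2.2.2 lists SpO2 among the vital signs and FiO2 among the treatment parameters taken at the Table 1 time points.

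The sample size in section 9.7.1.3 was computed "using the test for two proportions using the Z-test with unpooled variance". It uses no covariates and counts on no gain from any.

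**The concern.** How hypoxaemic a patient is at entry is a natural candidate predictor of intubation or death. The protocol itself links severe ARDS to high mortality (section 7.1) and uses a PaO2/FiO2 threshold to direct care after intubation (section 9.4.1). Mode of support is a device label and only a partial stand-in for severity.

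In a logistic model, leaving out a prognostic baseline variable does not invalidate the treatment test. It pulls the estimated effect towards the null relative to the conditional effect, and the Wald test loses some power. Both the interim and the final test are Wald tests from this model, so both would share the loss. The value that could recover it is measured before treatment and needs no new collection.

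**Working it through.** **1. Inputs.** Overall alpha: "Overall, an alpha of 0.025 one-sided will be spent on the primary outcome". Bounds: "One-sided significance bounds for the two analyses are 0.0026 and 0.024", that is, critical values 2.794 and 1.977. Power and size: "overall one-sided type-one error of 2.5% and statistical power of 80%, 171 patients per group (342 overall" in total. Event rates (Synopsis): 50% in control and 35% with the intervention. Allocation is 1:1, with the interim analysis at 50% of patients and negligible dropout expected (section 9.7.1.2.2.2).

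**2. Reproducing 342.** Fixed design, unpooled variance, per arm:

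n = [p1(1−p1) + p2(1−p2)] (1.960 + 0.842)² / (p1−p2)² = (0.25 + 0.2275) × 7.849 / 0.0225 = 166.6, or 333 in total.

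The inflation factor for a two-look O'Brien-Fleming design is 1.0078, so the total is 333.1 × 1.0078 = 336. With pooled variance the fixed total is 340, and 340 × 1.0078 = 343. Both are within 3% of 342. At 171 per arm the unpooled drift is 0.15 / √(0.4775/171) = 2.839, and two-look power is 80.7%.

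**3. The logistic Wald test without the ratio.** The log odds ratio is ln(0.35/0.65) = −0.619 (odds ratio 0.538). SE = √[(1/0.25 + 1/0.2275)/171] = 0.2216. Drift θ = 0.619/0.2216 = 2.794. Power is 1 − P(Z1 < 2.794, Z2 < 1.977), where (Z1, Z2) is bivariate normal with means θ√0.5 and θ and correlation √0.5. The result is 79.5%.

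**4. The same test with the ratio.** Let X be the standardised ratio, taken as normal, with logit P(event) = a + b·treatment + g·X and g = ln(odds ratio per SD). The values a and b are set so that the average event rates stay at 50% and 35%. The large-sample information matrix for (1, treatment, X) gives the SE of b at N = 342, and the drift is |b|/SE. The documents give no value for g, so it is varied:

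| Assumed OR per SD | Conditional treatment OR | Drift | Power at 342 | N giving the same drift as the unadjusted test |
|---|---|---|---|---|
| 1.0 | 0.538 | 2.794 | 79.5% | 342 |
| 1.25 | 0.534 | 2.809 | 79.9% | 338 |
| 1.5 | 0.526 | 2.843 | 80.8% | 330 |
| 2.0 | 0.504 | 2.927 | 83.0% | 312 |
| 2.5 | 0.483 | 3.010 | 85.1% | 295 |

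The comparator here contains no covariates, whereas the planned model contains age, mode and centre. The odds ratio per SD must therefore be read as the association that remains after those three.

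**5. Simulation check.** Separate logistic fits per stage were combined by the Inverse Normal method, 20,000 trials per setting. Power without and with the ratio was 79.7% and 80.2% (OR 1.25), 80.1% and 81.5% (1.5), 79.9% and 83.5% (2.0), 80.3% and 86.0% (2.5). One-sided type I error with the ratio was 0.0245 to 0.0268, with Monte Carlo SE √(0.025 × 0.975/20,000) = 0.0011. A smaller run of 6,000 trials, using spending-function bounds, gave 80.0% without and 79.7% with a non-prognostic ratio, which is no material difference. One setting of that run (OR 2.0) showed a type I error of 0.0307. The larger run gave 0.0245 at the same OR, so I read the 0.0307 as noise.

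**6. Sensitivity to the bounds.** Sections 9.7.1.2.2.1 and the Synopsis do not describe quite the same boundary: an O'Brien-Fleming type spending function gives 0.0015 and 0.0245. That is a separate matter. With those bounds the OR 2.0 comparison is 79.6% against 83.2%, the same gain of 3.6 points.

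**The case against.** The strongest reply is that nothing here is wrong. Adjusting for the stratification factors is standard and valid, the protocol gives that reason, and 342 does not rely on more. That stands, and it is why this is an improvement and not a correction.

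Second, the size rests on a prognostic strength that the documents do not supply. This also stands. At an odds ratio per SD of 1.5 or less the gain is under 1.5 points. Entry conditions narrow the spread as well: with FiO2 of at least 40%, SpO2/FiO2 cannot exceed 100/0.40 = 250, and patients in urgent need of intubation are excluded.

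Third, a reader might infer from the 79.5% that the trial is underpowered or has no margin. The documents do not support that. The protocol's own test gives 80.7%, and the sample size may be raised to 513 for a conditional power of 80%. Assuming no futility stop and a second stage of 171 to 342 patients, the unadjusted Wald test reaches 86.3% if conditional power uses the planned effect and 88.8% if it uses the observed effect. The protocol does not say which effect applies.

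A reader might also argue that sparse centre-by-mode-by-age strata make imbalance in oxygenation likely. They do not: the ratio is not a stratification factor, so its balance is that of ordinary randomisation, and the type I error already allows for chance imbalance. Nor does the protocol fix age as a dichotomy in the model, so its coding is not a fault.

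Finally, the wording on respiratory status in section 9.7.1.2.2.1 might be taken to cover oxygenation already. The same sentence ties it to the stratification, and section 9.4.2 and the Synopsis name mode of support, so that reading fails.

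**Conclusion.** The point holds as a missed gain in precision. The gain over 79.5% is 0.4, 1.3, 3.5 or 5.6 points at an assumed odds ratio per SD of 1.25, 1.5, 2.0 or 2.5 (from rounded powers), equivalent to about 4, 12, 30 or 47 patients. It is nil, with no material loss, if the ratio carries no information beyond age, mode and centre. These figures are for 342 patients without re-calculation and assume a roughly normal ratio with a linear effect on the logit. Confidence is medium: the omission and the validity of the change are clear from the documents, but the benefit rests on an assumed association. It is a nearly cost-free improvement; declining it would leave a sound primary analysis.

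**What to change.** Before any unblinded look, amend the Synopsis (Statistical analysis) and section 9.7.1.2.2.1, and carry the change into the SAP:

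- Add SpO2/FiO2 at randomisation as one continuous fixed effect in both stage-wise models. Use this ratio for everyone, because both components are scheduled at screening. Do not substitute PaO2/FiO2 where a blood gas exists, since that would put two scales into one covariate.
- State a simple rule for a missing baseline value, fixed in advance and blind to treatment and outcome.
- Keep age, mode of support and centre in the model and keep 342. Hold any gain as reserve.
- Use one term for mode of respiratory support in both places.

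The cost is a few lines of text and no new data. The one downside is interpretive: the odds ratio becomes conditional on one more covariate. At an odds ratio of 2.0 per SD, for example, the same 50% and 35% event rates correspond to 0.504 instead of 0.538, so the description of the effect measure should say what it is conditional on.

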	
 ○ days free from invasive mechanical ventilation or non-invasive ventilation at 28 days (defined as days alive without invasive/non-invasive ventilation) ○ days free from cardiovascular organ support (including vasopressors, catecholamines and mechanical circulatory support) ○ Differences in AHRF presumed origin 
 ▪ COVID-19 ▪ Influenza ▪ Hospital acquired pneumonia ▪ Community acquired pneumonia ▪ Pneumonia in immunosuppressed individuals ○ Differences of Devices used 
 ▪ HFNO ▪ NIV ▪ CPAP ▪ Combination of the above ○ Effect on Oxygenation after awake prone positioning 
 ▪ Improvement of spO₂ ▪ Improvement in Horowitz Index ▪ Respiratory Rate ○ days alive and outside the intensive care unit at 28-days ○ days alive and outside the hospital at 28-days ○ hospital and intensive care unit length of stay ○ Organ support 
 ▪ Rate and length of RRT ▪ Need for vv-ECMO ▪ Need for va-ECMO ○ APP Related events

Trial Design
	
Investigator-initiated, prospective, randomized, open, blinded endpoint assessment (PROBE) interventional multi-center, phase 4 trial. Adaptive design with an interim analysis and re-calculation of the sample size after follow-up of 50% of the planned sample size.
 
Eligible patients will be randomized (1:1) to standard awake prone positioning or standard supine/semi-recumbent positioning alone. Randomization will be stratified by centre, mode of ventilation at randomization, as well as age (below versus equal/ above 70 years) using block randomization with varying block sizes.

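### Secondary models adjust for centre only, although age and mode of respiratory support are also strata and the synopsis ties secondary analyses to the primary one

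*Protocol*

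**What the plan says.** The synopsis (Trial Design) and Section 9.4.2 stratify randomisation by centre, age (below 70 years versus 70 and above) and mode of respiratory support.

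The primary model carries all of these. The synopsis lists "age and mode of respiratory support at inclusion as fixed effects and centre as random effect in order to map the stratified randomisation scheme". Section 9.7.1.2.2.1 lists "age and respiratory status at randomization fixed effects and centre as random effect to reflect the stratified randomization". I read the two labels for the respiratory factor as the same variable.

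For the secondary endpoints the synopsis gives a general rule: "Secondary outcomes will be analysed depending on the scale type, corresponding to the primary analysis". Section 9.7.1.2.2.1 repeats the part about scale type, drops the link to the primary analysis, and specifies three models. Binary outcomes get this one: "Dichotomous variables will be tested by mixed logistic regression with centre as random effect". Event times get a Cox model whose only named adjustment is a frailty for centre. Outcomes on a continuous scale get a linear mixed model whose named terms are the outcome's baseline value and a random centre effect.

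On their status the section says: "P-values and confidence intervals derived from these analyses are of descriptive nature only".

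**The concern.** None of the three secondary models names age or mode of respiratory support. The primary model includes both for the express purpose of matching the randomisation scheme, and that reason applies equally to the secondary endpoints. Anyone drafting the analysis has two instructions: mirror the primary model (synopsis), or adjust for centre only (Section 9.7.1.2.2.1).

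The clearest consequence concerns 28-day death and 28-day intubation, the two components of the composite, which Section 8.3 lists as secondary endpoints. Odds and hazard ratios are non-collapsible: adding a prognostic covariate changes the quantity estimated even when the arms are balanced on it. Composite and components would stand side by side on different conditional scales. That is a difference in estimand, not a bias.

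Omitting prognostic strata also costs some power, and some precision for continuous outcomes. This applies mainly to the days-free and days-alive outcomes, which have no baseline value to adjust for.

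**Working it through.** **1. The plan's own figures (context only; none is disputed).** With 50% versus 35%, one-sided 2.5% and 80% power, the unpooled formula gives

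n per arm = (1.960 + 0.842)² × (0.50×0.50 + 0.35×0.65) / 0.15² = 166.6.

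With O'Brien-Fleming bounds at half the information this becomes 167.9 per arm, 336 in total, within 2% of the stated 342. Power at 171 per arm is 80.7%. The one-sided bounds 0.0026 and 0.024 are recovered. Changing the secondary models alters none of these.

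**2. Covariates side by side.**

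| Model | Centre | Age | Mode | Other adjustment |
|---|---|---|---|---|
| Primary, mixed logistic | random | fixed | fixed | none |
| Secondary, Cox | frailty | not named | not named | none |
| Secondary, logistic | random | not named | not named | none |
| Secondary, linear | random | not named | not named | baseline value |

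The primary model carries 3 of 3 strata, and each secondary model 1 of 3. This step needs no assumption.

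**3. Size, by simulation.** From the protocol: 342 patients, 20 planned sites, 50% versus 35%, 30% relative decrease. Assumed, because the protocol does not give them:

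- control risk 30% for death and 40% for intubation, hence 21% and 28% under intervention;
- age split 50/50, and HFNO/NIV/CPAP 50/35/15%;
- centre random-intercept SD 0.3;
- prognostic odds ratios for age/mode of 1/1, 1.5/1.5, 2/1.5 and 3/2.5.

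There were 3000 trials per scenario (1500 for the composite), with Wald tests at 1.96.

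*Scale.* The same composite data were fitted both ways; shortfall = 1 − ln(OR, centre only)/ln(OR, all strata).

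| Age/mode OR | OR, centre only | OR, all strata | Log-OR smaller by |
|---|---|---|---|
| 1/1 | 0.532 | 0.528 | 1% |
| 1.5/1.5 | 0.528 | 0.520 | 2% |
| 2/1.5 | 0.527 | 0.511 | 5% |
| 3/2.5 | 0.524 | 0.485 | 11% |

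*Power (%), centre only versus all strata* (Monte Carlo SE of the paired difference 0.2 to 0.5 points).

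| Age/mode OR | Death, logistic | Intubation, logistic | Intubation, Cox |
|---|---|---|---|
| 1/1 | 47.6 vs 47.9 | 65.2 vs 65.6 | 67.5 vs 67.8 |
| 1.5/1.5 | 49.2 vs 49.9 | 64.6 vs 65.3 | 68.5 vs 69.5 |
| 2/1.5 | 47.9 vs 49.5 | 64.9 vs 66.2 | 65.8 vs 67.8 |
| 3/2.5 | 49.1 vs 52.6 | 66.9 vs 70.6 | 65.8 vs 68.6 |

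*Type I error.* Two-sided, with centre only: 4.0% to 5.5% (SE 0.4), so no inflation.

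*Price of adjusting.* The SE of the component log odds ratio rises from 0.2353 to 0.2367 (0.6%) at the low end and from 0.2348 to 0.2492 (6.1%) at the high end. The Cox SE rises by 0.2% to 0.5%.

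**4. A simpler cross-check.** Setting: two balanced binary strata with equal prognostic odds ratios, no centre effect, conditional treatment odds ratio 0.54, control risk 50%. At prognostic odds ratios of 1.5, 2 and 3, power is 79.5, 76.5 and 69.8% without the strata and 80.4, 78.6 and 74.8% with them. The direction is the same.

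**5. Continuous outcomes.** If the strata explain a share R² of the variance left after centre and any baseline value, intervals without them are wider by the factor 1/√(1 − R²): 1.026 at an assumed R² of 0.05, 1.054 at 0.10, and 1 at 0.

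**6. Sparse outcomes.** At assumed ECMO rates of 1%, 2% and 5%, 342 patients yield about 3, 7 and 17 events. Treatment, age and two mode terms make four parameters, so 0.9, 1.7 and 4.3 events per parameter. A mode level with 15% of patients (about 51) has no event with probability (1 − rate)⁵¹ = 60%, 36% and 7%. Full adjustment is fragile there.

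**The case against.** The strongest reply is that Section 9.7.1.2.2.1 is shorthand. Its secondary sentences do not even name the treatment term, and nothing says the lists are complete. The synopsis rule could supply age and mode, and a statistical analysis plan (not available here) could spell them out. That reading is possible, but it does not settle the matter. The section names adjustment terms model by model, including the frailty and the baseline value, so the natural reading is centre only, and the missing words are needed even if the synopsis governs.

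Several further points stand:

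- Equal covariates would not make composite and components fully alike. The composite estimate is the midpoint of a repeated confidence interval, whereas the secondary effects get ordinary 95% intervals.
- The sizes rest on assumed prognostic strengths. Even with non-prognostic strata, adjusting shows 0.3 to 0.5 points of power and a 1% shift, which is finite-sample behaviour rather than recovered information. Net of this, the gain at 1.5/1.5 is within about two Monte Carlo SEs for death and logistic intubation. The 11% and the gains near 4 points need the strongest scenario.
- Section 8.3 does not label intubation as time-to-event, and the Cox simulation ignores death as a competing event, so the Cox figures are illustrative.
- A uniform centre-only model is a defensible choice for descriptive outcomes, if stated as such and matched in the synopsis.

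These points limit the weight of the concern; they do not remove the disagreement between the two places.

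**Conclusion.** The concern holds and is minor. That the secondary models omit two of the three strata, and that this does not match the synopsis, follows from the text alone. The size depends on the assumptions in the simulation: with prognostic strata, a centre-only log odds ratio about 2% to 11% smaller and about 1 to 4 points of power lost on the components; with non-prognostic strata, practically nothing. Continuous outcomes lose about 3% to 5% in interval width if the strata explain 5% to 10% of the remaining variance. There is no bias, no inflation of type I error, and no effect on the primary test, alpha or sample size.

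**What to change.** In Section 9.7.1.2.2.1, state that the secondary Cox, logistic and linear models include age and mode of respiratory support at randomisation as fixed effects, coded as in the primary model, with centre as random effect (frailty in the Cox model). Label the resulting odds and hazard ratios as conditional on these factors. Allow a reduced model (treatment and centre, or treatment alone) for sparse outcomes such as need for vv- or va-ECMO, and fix before unblinding which outcomes take which reduction. If centre-only adjustment is intended, amend the synopsis instead and give the reason.

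The change takes one or two sentences and needs no new data, patients or alpha, since both variables are recorded at randomisation. It is not quite free: the SE of the component log odds ratio rises by about 1% to 6%, the ratios become conditional on two more factors, and rare outcomes need the reduced model.
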